11.6 Intensive Care Unit (ICU) Discharges

The time until discharge from ICU will be compared between groups with observation time up to 90 days. The total time from first administration of study drug will be taken from Study Drug Administration eCRF (dataset EX, First IP administration date). The date/time that subjects were admitted and discharged from ICU (from last hospitalization) will be taken from the Hospitalization eCRF page (dataset: AEHO).

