3.2 Study Endpoints

- All-cause mortality.
- Ordinal Scale of Clinical Improvement, absolute values and changes from start of treatment to Days 2, 3, 7, 15, and 30.
- Time to a 1-point decrease on the Ordinal Scale of Clinical Improvement from start of treatment.

- Area under the severity versus time curve, where severity is defined by the Ordinal Scale of Clinical Improvement and time is measured from start of treatment to Days 2, 3, 7, 15, and 30.
- Days of supplemental oxygen or mechanical ventilation from start of treatment (up to 90 days).
- First Intensive Care Unit (ICU) discharge
- Days in ICU from start of treatment (up to 90 days).
- Discharge from hospital.
- Days hospitalized from start of treatment (up to 90 days).
- Severity of ARDS as defined by the Berlin criteria, absolute values and changes from start of treatment to Days 2, 3, 7, 15, and 30.
- Cytokine and biomarker results, absolute values and changes from start of treatment to Days 2, 3, 7, 15, and 30.
- Adverse events (AEs) and serious adverse events (SAEs) within 90 days from start of treatment.

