11.4 Ordinal Scale of Clinical Improvement, AUC Analysis

The computation of Area Under the Curve (AUC) provides a method to combine multiple timepoints of Ordinal Scale of Clinical Improvement within a specific time interval, into a single index. AUCs will be calculated using SAS macros incorporating the “trapezoidal rule” to compute the area of each individual small trapezoid whereby the total sum of those individual areas equals the total area under the curve (i.e., total AUC) for that time period.

In order to examine clinical improvement trends over the entire visit period from time points $t=$ Day 1 to $t=$ Day 90, the total AUC will be calculated by summing each individual trapezoid (Day 1 to Day 2, Day 2 to Day 3, Day 3 to Day 7, Day 7 to Day 15, Day 15 to Day 30, Day 30 to Day 60, and Day 60 to Day 90) for each treatment group. The resulting AUCs will be summarized descriptively using N, mean, standard deviation, median, range.

The AUCs of clinical improvement will be analyzed using a MMRM as described above (see Section 11.2).

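### SAP 11.6 takes ICU dates from the last hospitalization although the endpoint is first ICU discharge, and SAP 11.4 does not commit to the declared AUC horizons

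*SAP*

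**What the plan says.** **ICU discharge.** SAP 3.2, matching Protocol 3, lists the endpoint "First Intensive Care Unit (ICU) discharge". SAP 11.6 compares time to ICU discharge over up to 90 days from infusion and gives the date source: "The date/time that subjects were admitted and discharged from ICU (from last hospitalization) will be taken from the Hospitalization eCRF page".

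**Ordinal-scale AUC.** For this endpoint SAP 3.2 says "time is measured from start of treatment to Days 2, 3, 7, 15, and 30". SAP 11.4 defines AUC in general terms for any interval. It then says that, over Day 1 to Day 90, "the total AUC will be calculated by summing each individual trapezoid". It closes with "The AUCs of clinical improvement will be analyzed using a MMRM as described above", pointing back to 11.2.

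**ICU and hospital durations.** SAP 3.2 counts both from the start of treatment, to a maximum of 90 days. SAP 11.7 and 11.9 each give two definitions. The first runs from admission; the second is tied to admission after study drug. Neither is named as the 3.2 endpoint. Each section also has a sentence imputing an extreme value to subjects without a documented discharge. Numbered rules for death, withdrawal and database lock follow it.

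SAP 14 lists no change of endpoint that would explain any of these differences.

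**The concern.** The derivation sections are what the programmer follows. In 11.6 that instruction selects a different event from the declared one whenever an earlier hospitalization contains the first ICU discharge after infusion. The error is at the level of the subject: a short time to discharge becomes a long one, or disappears.

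In 11.4 the risk is of another kind. The only AUC that the section undertakes to produce is one that 3.2 does not list, and the five that 3.2 does list have no stated analysis. One total per subject is not a repeated measure, so the model named for it is not defined. This leaves horizon and model to be settled later, in a plan that describes all its analyses as prespecified (SAP 9).

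**Working it through.** The documents contain no figure to reproduce here. The check sets the endpoint list against the derivations and works small examples. All example dates and scores are invented.

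**1. ICU discharge.** Protocol 8.2.8 collects the index and any later hospitalization, and Protocol 8.2.9 collects all ICU admission and discharge dates. First and last can therefore differ, and the data can tell them apart. Times below are days after infusion.

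| Case | Endpoint in 3.2 | Result from 11.6 |
|---|---|---|
| ICU discharge at 5; second hospitalization with ICU stay ending at 50 | 5 | 50 |
| ICU discharge at 5; second hospitalization on the ward only | 5 | no date |
| Rehospitalized; only ICU stay is in the last hospitalization | that discharge | same |
| Rehospitalized; never in ICU | none | none |
| One hospitalization, one ICU stay | that discharge | same |
| Several ICU stays within one hospitalization | the first after infusion | not stated |

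The documents give no rehospitalization rate. SAP 4 plans for up to 60 treated subjects. Assuming 5% to 15%: 0.05 × 60 = 3 and 0.15 × 60 = 9. Because of rows three and four, 3 to 9 is an upper bound on the subjects given a wrong or missing date through rehospitalization.

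**2. AUC.** The 11.4 visit grid is Days 1, 2, 3, 7, 15, 30, 60 and 90.
- Length of the 11.4 total: 90 − 1 = 89 days.
- Lengths of the declared horizons: 1, 2, 6, 14 and 29 days.
- Share of the total lying after Day 30: 60/89 = 67.4%.
- A constant 1-point difference is worth 29 AUC units over Days 1 to 30 and 60 units over Days 30 to 90; 60/29 = 2.07.

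To see whether the choice of horizon can matter, take two score paths on that grid: A = 5, 5, 4, 3, 2, 2, 2, 2 and B = 5, 5, 5, 5, 4, 2, 1, 1. Cumulative trapezoid sums:

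| To Day | 2 | 3 | 7 | 15 | 30 | 60 | 90 |
|---|---|---|---|---|---|---|---|
| A | 5 | 9.5 | 23.5 | 43.5 | 73.5 | 133.5 | 193.5 |
| B | 5 | 10 | 30 | 66 | 111 | 156 | 186 |

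A is better at Day 30 (73.5 against 111) and slightly worse at Day 90 (193.5 against 186; 7.5/193.5 = 3.9%). A reversal is possible; the example says nothing about how likely it is. The table also shows that every declared AUC is a partial sum of trapezoids that 11.4 already lists.

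**3. Durations.** With infusion at 0, take an index stay from −4 to 10 and a readmission from 40 to 46.
- Time from start of treatment, as in 3.2: 10 + 6 = 16 days.
- Definition (1): 14 + 6 = 20 days, including 4 days before infusion.
- Definition (2), read as time after dosing: 16 days.

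Only definition (2), read that way, matches 3.2.

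**The case against.** The strongest reply is that much of this is wording rather than error. Several stronger readings should indeed be set aside.

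- **11.6.** The word for last may have been meant as the current or index stay. The text does not say so, and the protocol expects later admissions, so the contradiction stands. A reader might infer that every rehospitalized subject is wrong and everyone else is safe. Neither follows: some rehospitalized subjects are unaffected, and several ICU stays within one hospitalization are left undefined.
- **11.4.** A reader might infer that the Day 90 total replaces the declared endpoint. It does not say that. The general definition, the plural AUCs and trapezoid boundaries at each declared day all allow the five horizons, and the total is introduced separately, for trends over the whole visit period. What stands is that the declared horizons are not committed to and the repeated factor is not named. The 2.07 weighting and the reversal bite only if the total is reported in their place.
- **Definition (2).** Read literally it counts only admissions after dosing, giving 6 days instead of 16 above and dropping the index hospital stay. That is implausible. Dosing is inpatient (Protocol 6.4), the rule for subjects hospitalized throughout follow-up would lose its purpose, and 11.5 contrasts time before and after study drug. The days before infusion in definition (1) cannot be affected by treatment; under blinded randomization they add noise, not bias between arms.
- **Imputation.** One could read the extreme-value sentence as overriding the rules, so that a death in ICU 5 days after infusion scores 90 rather than 5. The specific rules come directly after it and naturally govern.
- **SAP 14.** Bringing Section 11 into line with 3.2 removes a difference from the protocol; it does not create one to be declared.

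**Conclusion.** The 11.6 point holds as a direct contradiction with SAP 3.2 and Protocol 3. It gives a wrong or missing first ICU discharge for subjects with an ICU discharge after infusion in one hospitalization and a later rehospitalization. The number is unknown; 3 to 9 of 60 is an upper bound resting on an assumed 5% to 15% rate.

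The AUC point holds as incomplete specification: five declared horizons without a stated analysis, one undeclared total with 67.4% of its time after Day 30, and a repeated-measures model without a defined repeated value.

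The duration and imputation points are minor clarifications. With no formal sample size calculation and p-values used descriptively (SAP 4 and 11), none of this threatens a confirmatory test. All of it should be corrected before unblinding.

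**What to change.** 1. **11.6:** replace the reference to the last hospitalization with the first ICU discharge after infusion, taken across all hospitalizations. This also settles the case of several ICU stays in one hospitalization.
2. **11.4:** compute and report AUC from Day 1 to each of Days 2, 3, 7, 15 and 30, as partial sums of the listed trapezoids. Give the treatment contrast at each horizon with the 11.2 covariates. State whether this is one model per horizon or a single model with horizon as the repeated factor. Keep the Day 90 total as supplementary.
3. **11.7 and 11.9 (clarification):** reword definition (2) as time in ICU or hospital after infusion, including the post-infusion part of a stay in progress at dosing and capped at 90 days. In elapsed days, sum over stays max(0, min(end, infusion + 90) − max(admission, infusion)), where end is discharge or the date set by numbered rules (2) to (5). Name it as the 3.2 endpoint and keep definition (1) as descriptive.
4. **11.7 and 11.9 (clarification):** state that the numbered rules govern over the extreme-value sentence for death, withdrawal and database lock.
5. **SAP 14:** at most, note the supplementary Day 90 AUC.

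The cost is SAP wording and derivation code. The stay dates (Protocol 8.2.8 and 8.2.9) and the ordinal scores (Protocol 1.3) are already scheduled for collection.

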11.7 Days in ICU and Time to Discharge

Duration in the ICU (days) will be defined in two ways:

- (1) The interval from the subject’s date/time of ICU admission to the date/time the subject is discharged from the ICU (Hospitalization dataset: AEHO). If a subject is admitted to the ICU multiple times, then all ICU visits will be added together to calculate the duration in ICU.
- (2) The interval from the subject’s date/time of ICU admission after study drug administration to the date/time the subject is discharged from the ICU (Hospitalization dataset: AEHO). If a subject was admitted to the ICU multiple times, then all ICU visits will be added together to calculate the duration in ICU.

Those subjects that were not admitted to the ICU or have no documentation of being discharged from the ICU will be censored for time to event analysis and will be imputed as the highest or lowest score for purposes of continuous outcome analysis.

The following censoring/ imputation rules will be followed:

- (1) If subjects do not have a documented admittance into the ICU, the duration in ICU will be censored at Day 1, or an imputed score of zero.
- (2) If subjects are in ICU through the entire follow-up phase, then the duration in ICU will be censored at the end of study date (maximum of 90 days), or imputed as the days in the study.
- (3) If subjects die while in ICU, then the duration in ICU will be censored at the date of death, or imputed as the days until death.
- (4) If subjects withdraw from study (any reason) while in the ICU, then duration in ICU will be censored at the date of study withdrawal or imputed as the number of days until withdrawal.
- (5) If subjects are in ICU at the time of database lock and analysis (unlikely, but possible), the duration in ICU will be censored on the date of database lock or imputed as the number of days until database lock.

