## **3 OBJECTIVES AND ENDPOINTS**

The primary objectives of the study are to determine the safety and effectiveness of intravenously infused CAP-1002 in improving clinical outcomes in severely or critically ill patients with COVID-19.

Several exploratory safety and efficacy endpoints will be measured to evaluate the effects of CAP-1002 treatment on the morbidity and mortality of severely or critically ill patients with COVID-19. The endpoints are as follows:

- All-cause mortality.
- Ordinal Scale of Clinical Improvement, absolute values, and changes from start of treatment to Days 2, 3, 7, 15, and 30.
- Time to a 1-point decrease on the Ordinal Scale of Clinical Improvement from start of treatment.
- Area under the severity versus time curve, where severity is defined by the Ordinal Scale of Clinical Improvement and time is measured from start of treatment to Days 2, 3, 7, 15, and 30.
- Days of supplemental oxygen or mechanical ventilation from start of treatment (up to 90 days).
- First Intensive Care Unit (ICU) discharge
- Days in ICU from start of treatment (up to 90 days).
- Discharge from hospital.
- Days hospitalized from start of treatment (up to 90 days).

- Severity of ARDS as defined by the Berlin criteria, absolute values, and changes from start of treatment to Days 2, 3, 7, 15, and 30.
- Cytokine and biomarker results, absolute values, and changes from start of treatment to Days 2, 3, 7, 15, and 30.
- Adverse events (AEs) and serious adverse events (SAEs) within 90 days from start of treatment.

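### Time to ICU discharge drops subjects who never enter the ICU, so averting mild admissions can read as harm; separately, the ICU day count scores an early ICU death as a short stay.

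*SAP*

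**What the plan says.** Two of the listed endpoints concern the ICU: first ICU discharge, and "Days in ICU from start of treatment (up to 90 days") (Protocol 3, repeated in SAP 3.2). For the first, SAP 11.6 states: "The time until discharge from ICU will be compared between groups with observation time up to 90 days". SAP 11 makes a Cox model adjusted for a baseline risk score, with Kaplan-Meier curves and a log-rank test, the primary analysis of each efficacy endpoint unless the endpoint's own section says otherwise.

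SAP 11.7 then gives each special case two treatments, one for a time-to-event analysis and one for a continuous analysis:

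- Never admitted, rule (1): "If subjects do not have a documented admittance into the ICU, the duration in ICU will be censored at Day 1"; for the continuous analysis the same rule gives these subjects a score of zero.
- Death in the ICU, rule (3): "then the duration in ICU will be censored at the date of death, or imputed as the days until death".
- Withdrawal in the ICU, rule (4): "then duration in ICU will be censored at the date of study withdrawal or imputed as the number of days until withdrawal".

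A general sentence above these rules says that subjects with no ICU admission, or with no documented ICU discharge, "will be imputed as the highest or lowest score for purposes of continuous outcome analysis" in the continuous case. The section does not say which of the two analyses is the main one.

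**The concern.** Never needing the ICU is the best ICU outcome a subject can have. Censoring it at Day 1 gives it no weight in the Cox model or the log-rank test. What remains is a comparison of subjects who had an ICU stay. For anyone outside the ICU at infusion, having a stay happens after randomisation and may depend on treatment, so the randomised comparison is lost. If treatment keeps the milder cases out, the treated subjects left in the comparison are the sicker ones and leave the ICU more slowly.

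The day count has a different fault. Fewer days counts as better, yet a stay cut short by death or withdrawal is entered as if it were complete. Rule (1) also makes no exception for a subject who dies without entering the ICU, who would score zero.

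The p-values are descriptive, but the multiplicity text under SAP 9.3 judges proof of concept on the totality of evidence across endpoints. An ICU result with the wrong sign would enter that judgement.

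**Working it through.** The plan gives no ICU admission rate, length of stay, effect size or significance level, so there is no stated figure to reproduce.

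**Step 1: can a subject be never admitted?** Protocol 5.1 requires oxygen saturation below 94% or COVID-19 cardiomyopathy, plus a raised inflammatory marker. It does not require ICU care. Protocol 5.2 excludes intubated patients, and the SAP has a rule for subjects without an ICU admission. Against this, Protocol 6.6 presupposes that every patient is cared for in an ICU. The documents do not settle how large the group is.

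**Step 2: what censoring at Day 1 does.** The Cox partial likelihood is a product, over discharge times t, of exp(βz_i) / Σ_{j in R(t)} exp(βz_j), where R(t) holds the subjects still under observation at t. A subject censored at Day 1 is in no R(t) for any later discharge and has no event, so contributes nothing to either the Cox model or the log-rank test.

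**Step 3: worked example (assumed numbers, 30 per arm).** In the control arm, 20 are admitted: 10 stay about 5 days and 10 about 20 days. The drug averts the 10 short stays and changes nothing else.

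- Early discharges: all 10 are controls, with 10 treated subjects among 30, 29, …, 21 at risk. Expected treated discharges = 10 × (1/30 + 1/29 + … + 1/21) = 3.97; observed = 0; variance = 2.37.
- Late discharges: the arms match, so observed equals expected; variance = 3.93.
- Log-rank z = −3.97 / √(2.37 + 3.93) = −1.58, p = 0.11. The Cox hazard ratio for discharge is 0.57, and it is still 0.57 if the never-admitted subjects are deleted from the data.
- Median stay among those admitted: 12.5 days (control) against 20 days (drug).
- Day count with never admitted = 0: control (10 × 5 + 10 × 20)/30 = 8.3 days; drug (10 × 20)/30 = 6.7 days.

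The same data give harm on one branch and benefit on the other.

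**Step 4: simulation (1,500 trials per scenario).** Assumptions, none from the documents: 30 per arm; control ICU admission 40%, 60% or 80%; 25% or 50% of admissions averted, either the mildest or at random; stay linked to severity with a median of about 10 days; ICU mortality about 25%; no drug effect on stay once admitted; unadjusted Cox model; two-sided 0.05. The ranges run over the three admission rates.

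| Admissions averted | Median discharge HR, SAP rule | HR below 1 | Nominal harm | Nominal benefit | Change in mean ICU days |
|---|---|---|---|---|---|
| Mildest 25% | 0.77–0.79 | 67–77% | 6–12% | 0.3–1.1% | −0.7 to −1.2 |
| Mildest 50% | 0.54–0.59 | 80–94% | 13–28% | 0–0.3% | −1.5 to −2.6 |
| Random 25% or 50% | 1.00–1.05 | 47–50% | 2–3% | 2.5–5% | −1.1 to −4.8 |
| None (60% admitted) | 1.00 | 50% | 3% | 3% | 0.0 |

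Counting never-admitted subjects as out of the ICU at time 0, and holding ICU deaths to Day 90 without discharge, moves the median hazard ratio in the mildest-averted scenarios to 1.08–1.38. In the same scenarios, 30-day ICU-free days with ICU death scored worst favour the drug by 1.3 to 4.9 days.

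**Step 5: death and withdrawal in the day count.** Under rule (3) a subject who dies after 5 days in the ICU scores 5, better than a survivor discharged after 20. In the simulation with 60% admitted and no effect on admission, doubling ICU mortality from a 20% base lowers mean ICU days by 1.1, so the more lethal arm looks better. Rule (4) treats withdrawal the same way. Neither score is generally the highest or lowest possible, although both kinds of subject lack a documented discharge and so fall under the general sentence.

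**The case against.** The strongest reply is that rule (1) has a second half. In the continuous analysis never-admitted subjects score zero, and preventing admission looks beneficial in every prevention scenario above. SAP 11 also makes Cox only a default, and SAP 11.7 offers both branches. This stands: a reader might infer that the planned ICU analyses as a whole turn prevention into harm, and the documents do not support that. The fault belongs to the time-to-event branch, chiefly the first-discharge endpoint. What remains is that the branches can contradict each other and neither is named as leading.

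Second, apparent harm needs selective prevention of milder cases. This also stands; with random prevention the benefit is hidden but not reversed.

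Third, adjustment for the baseline risk score might absorb the selection. It may help, but the components listed in SAP 11 are age, weight, sex and comorbidities. None measures oxygen need or acute severity, so it cannot be relied on.

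Fourth, if Protocol 6.6 is literally true and all subjects are in the ICU at infusion, the never-admitted problem is small. This stands as a condition, and for those subjects ICU status is a baseline fact.

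Fifth, a reader might link the withdrawal rule to the apparent harm. It does not contribute: in the time-to-event analysis withdrawals are already censored. Its day-count score, "imputed as the number of days until withdrawal", favours whichever arm has more or earlier ICU withdrawals, and it is a short stay only when withdrawal is early.

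**Conclusion.** The SAP is wrong as written on two separate counts.

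1. In the time-to-event analysis, censoring never-admitted subjects at Day 1 restricts the comparison to subjects with an ICU stay. Under the assumed inputs the median discharge hazard ratio is 0.54–0.79 if the mildest admissions are averted and about 1.00–1.05 if they are averted at random. The loss of never-admitted subjects from the comparison follows from the SAP text; the sizes, and whether the result reverses or merely hides a benefit, rest on the assumptions. The size of the affected group depends on reconciling Protocol 6.6 with rule (1).
2. In the day count, rules (3) and (4) score death or withdrawal in the ICU as a completed stay. Early ICU death then looks favourable, and the rules conflict with the general sentence in the same section.

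This should be fixed before unblinding but does not invalidate the trial. The study is an exploratory pilot without a formal sample size, p-values are descriptive, and mortality and the ordinal scale (death = 8) are analysed separately.

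**What to change.** - Make days alive and out of the ICU from infusion to Day 90, with deaths scored 0, the main ICU analysis in all mITT subjects, compared by ranks. A survivor never admitted then scores 90, a survivor with 20 ICU days scores 90 − 20 = 70, and a death scores 0. The 30-day measure in the working is a close relative of this endpoint; the 90-day version itself was not simulated.
- Limit time to first ICU discharge to subjects in the ICU at infusion. Treat ICU death as never discharged (held to Day 90) instead of censoring at death.
- Keep the existing censoring of withdrawals in the time-to-event analysis. In the day count, do not score withdrawal as a completed stay; multiple imputation is optional.
- Remove the general highest-or-lowest sentence or align it with the numbered rules, and state which ICU analysis leads.
- Reconcile Protocol 6.6 with SAP 11.7 rule (1), and report how many subjects in each arm were in the ICU at infusion.

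The cost is SAP wording and one derived variable. ICU admission and discharge dates (Protocol 8.2.9, SAP 11.6) and death dates (SAP 11.1) are already collected.

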11. EFFICACY ANALYSIS

The modified Intent-to-Treat Population (as Treated) is defined as all enrolled and randomized subjects who received any amount of study treatment; the mITT population will be utilized for all efficacy analyses. All summary tables will be displayed by treatment arm.

This is a Phase 2 proof of concept study, so a hierarchical testing order will be specified, but p-values will be utilized for descriptive purposes even if a step in the hierarchy is not met and there will be no adjustment for multiplicity of analyses. In addition to the analysis by severity of COVID risk at baseline, additional subgroup analyses will be conducted on an ad-hoc basis and will be fully described in the clinical study report.

The primary analysis for each efficacy endpoint will be as follows, unless otherwise noted in the corresponding section. A Cox Proportional Hazards (PH) model will be utilized to characterize overall survival or time-to-event, correcting for baseline COVID severity risk score. This risk score will be calculated based on historical data and will include baseline characteristics of age, weight, sex, and presence of comorbidities. In addition, unadjusted Kaplan-Meier curves will be presented by treatment group and summary statistics will include estimates of median survival (and corresponding 95% confidence interval), minimum and maximum time, and the number of censored subjects. The overall survival time will be compared between the treatment arms using a log-rank test.

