11.5 Time on Supplemental Oxygen or Mechanical Ventilation

The total time (days) on respiratory/ventilator (mechanical) support will be taken from the Respiratory/Ventilator eCRF page (dataset: QS1). The time will be calculated from the date/time that the subject required respiratory/ventilator support (eCRF checked “Yes” for this question) to the date/time that the subject did not need respiratory/ventilator support (eCRF checked “No” for this question). If a subject had multiple occurrences of needing mechanical support, then these times will be summed together.

Time on mechanical ventilation will be defined in two ways:

- (1) The interval from the subject’s date/time of the original mechanical ventilation collected (could be prior to study drug administration) to the date/time the subject is off mechanical ventilation. If a subject had multiple occurrences of needing mechanical support, then these times will be summed together.
- (2) The interval from the subject’s date/time of mechanical ventilation after study drug administration to the date/time the subject is off mechanical ventilation. If a subject had multiple occurrences of needing mechanical support, then these times will be summed together.

The censoring/imputation rules as defined above will be followed.

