11.9 Duration of Hospitalization

Duration of hospitalization (days) will be defined in two ways:

- (1) The interval from the subject's date/time of hospital admission to the date/time the subject is discharged from the hospital (Hospitalization dataset: AEHO). If a subject is

hospitalized multiple times, then all hospitalizations will be added together to calculate the duration of hospitalization.

(2) The interval from the subject's date/time of hospital admission after study drug administration to the date/time the subject is discharged from hospital (Hospitalization dataset: AEHO). If a subject is hospitalized multiple times, then all hospitalizations will be added together to calculate the duration of hospitalization.

Those subjects that were not admitted to hospital or have no documentation of being discharged from the hospital will be censored for time to event analysis and will be imputed as the highest or lowest score for purposes of continuous analysis.

The same censoring/imputation rules as outlined above for ICU will be followed:

- (1) If subjects do not have a documented admittance into the hospital, the duration of hospitalization will be censored at Day 1.
- (2) If subjects are in the hospital through the entire follow-up phase, then the duration of hospitalization will be censored at the end of study date (maximum of 90 days).
- (3) If subjects die while in the hospital, then the duration of hospitalization will be censored at the date of death.
- (4) If subjects withdraw from study (any reason) while in the hospital, then duration of hospitalization will be censored at the date of study withdrawal.
- (5) If subjects are in hospital at the time of database lock and analysis (unlikely, but possible), the duration of hospitalization will be censored on the date of database lock.

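### ICU days score an early death as a short, favourable stay, and Kaplan-Meier curves of discharge censor deaths and so overstate discharge

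*SAP*

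**What the plan says.** SAP 3.2 lists days in ICU, first ICU discharge, days hospitalized and hospital discharge among the endpoints.

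- **Death in ICU** (11.7, rule 3): "the duration in ICU will be censored at the date of death, or imputed as the days until death".
- **No documented ICU admission** (11.7, rule 1): "the duration in ICU will be censored at Day 1, or an imputed score of zero". The rule does not look at vital status.
- **In ICU throughout follow-up** (11.7, rule 2): censored at the end of study, "or imputed as the days in the study".
- **Lead-in to these rules**: subjects not admitted, or with no documented discharge, "will be imputed as the highest or lowest score for purposes of continuous outcome analysis". It does not say who gets which.
- **Hospital stay** (11.9): "The same censoring/imputation rules as outlined above for ICU will be followed", but the printed rules only censor: "If subjects die while in the hospital, then the duration of hospitalization will be censored at the date of death".
- **Time on oxygen or ventilation** (11.5): "The censoring/imputation rules as defined above will be followed". The only imputation rules for days come later, in 11.7.
- **Default analysis** (11): "A Cox Proportional Hazards (PH) model will be utilized to characterize overall survival or time-to-event", with Kaplan-Meier curves, medians and a log-rank test.

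Neither document mentions competing risks, cumulative incidence or a worst score for death.

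**The concern.** Fewer ICU days are meant to be good. Under rule 3 a subject who dies on Day 5 scores 5 and a survivor who leaves the ICU on Day 14 scores 14, so the death looks better. Under rule 1 a subject who dies without entering the ICU scores zero, the best possible value. An arm with more early deaths can then look as good on stay as the other arm, or better.

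For time to discharge, censoring at death treats a dead subject as someone who could still have been discharged later. The cause-specific hazard from Cox or log-rank keeps a clear meaning. The Kaplan-Meier curve and median do not: they estimate discharge as if nobody died. SAP 9.3 will weigh the totality of evidence across endpoints, so a stay result that masks deaths would enter that judgement.

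**Working it through.** There is no planned figure to reproduce: SAP 4 gives no formal sample size calculation, and the documents give no mortality, stay or ICU-use rates. From the documents come about 30 per arm (SAP 4), 90 days of follow-up and the scoring rules. Everything else below is assumed, including arm means and a t-test, because the SAP names no test for the continuous analysis.

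**1. Direction.** With mortality m,

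arm mean = (1 − m) × mean survivor score + m × mean days until death,

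so the shift in arm mean = extra mortality × (mean days until death − mean survivor score). More deaths shorten the mean whenever deaths come earlier than the average survivor score, zeros included.

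Example: mortality 20% v 40%, survivors 14 days, death after 5 days.
- All survivors use ICU: 0.8 × 14 + 0.2 × 5 = 12.2 v 0.6 × 14 + 0.4 × 5 = 10.4, a shift of −1.8 days.
- Half of survivors at zero (mean 7): 0.8 × 7 + 0.2 × 5 = 6.6 v 0.6 × 7 + 0.4 × 5 = 6.2, a shift of −0.4 days.

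**2. Simulation, ICU days.** 10,000 trials, 30 per arm, 40% v 20% mortality. Survivor stay is lognormal (median 12 days, log-SD 0.6) in both arms. Death time is lognormal (median Day 6, 12 or 20, log-SD 0.5). Both are capped at 90. Entries are % of trials for median death Day 6 / 12 / 20.

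| Survivors scored zero | Deadlier arm has shorter mean stay | Significant t-test for it | Significant t-test against it |
|---|---|---|---|
| 0% | 75 / 52 / 27 | 11 / 3 / 0.4 | 0.3 / 2 / 9 |
| 25% | 63 / 41 / 22 | 5 / 1 / 0.2 | 1 / 4 / 12 |
| 50% | 52 / 30 / 16 | 2 / 0.5 / 0.1 | 2 / 8 / 16 |

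In the first results column 50% means the arms look alike; in the other two, 2.5% is chance.

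- If 25% of deaths also score zero, the first results column in the last two rows becomes 69 / 52 / 35 and 58 / 40 / 26.
- At 30% v 20% mortality that column is 63 / 51 / 37, 56 / 45 / 34 and 50 / 39 / 31.
- With every death scored 90 and a rank-sum test, a significant result against the deadlier arm occurs in about 27 to 29% of trials in every row at 40% v 20%, and in about 9 to 10% at 30% v 20%.

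**3. Time to discharge.** Same distributions, all survivors in ICU (or hospital), 20% v 40% mortality. The true proportion discharged alive by Day 30 is 75 v 56%. The median with deaths kept as not discharged is 14.5 v 21.4 days.

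| Median day of death | Kaplan-Meier discharge by Day 30 | Kaplan-Meier median (days) | Hazard ratio, deaths censored | Hazard ratio, deaths kept to Day 90 |
|---|---|---|---|---|
| 6 | 93 v 92% | 12.6 v 13.3 | 0.93 | 0.61 |
| 12 | 90 v 83% | 13.6 v 16.0 | 0.76 | 0.60 |
| 20 | 83 v 68% | 14.2 v 18.6 | 0.66 | 0.61 |

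The true gap is 75 − 56 = 19 points. Kaplan-Meier shows 1, 7 and 15 points, so it hides about 95%, 65% and 20% of the gap.

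**4. Different model.** Take constant hazards with the same discharge hazard in both arms (0.05 per day). Survivors in the deadlier arm then also leave sooner. At 20% and 40% ICU deaths:
- mean ICU days under the SAP score are 15.9 and 12.0; with deaths scored 90 they are 30.8 and 43.2;
- Kaplan-Meier discharge by Day 30 is 77.7% in both, where the true figures are 67.7% and 55.1%;
- with 30 per arm, the deadlier arm has the shorter mean stay in about 87% of trials, and a significant rank test in its favour in about 15%. Scoring deaths as 90 gives a significant result against it in about 14%.

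**The case against.** **The continuous analysis is thinly specified and the direction is not fixed.** This stands. SAP 11.7 mentions it without naming a test, and late deaths or many survivors without ICU admission reverse the bias. Protocol 6.6 says all patients will be managed in an ICU, yet Protocol 5.2 excludes intubated patients, so the share is unknown. For hospital days under definition 1 of 11.9 this dilution should not arise, because treatment is given to inpatients (Protocol 6.4).

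**Harm is visible elsewhere.** This also stands. Mortality is the first listed endpoint with its own analysis (SAP 11.1). Under the same 40% v 20% assumption a log-rank test on mortality detects the harm in about 39% of trials, more than the worst-value rank test on ICU days. The gain from the change is a stay result that does not mislead, not a better detector of harm. The 30-day hospital discharge proportion (11.8) is unaffected, and p-values are descriptive.

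**Observed days are the literal endpoint, and a worst score replaces them with a composite.** True, and both are useful if labelled. But an unlabelled between-arm comparison of observed days cannot be read as benefit when deaths shorten the stay.

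**The lead-in could mean that deaths get the highest score.** It could, but rule 3 is specific and gives another value. The two sentences conflict, which is itself a reason to edit them.

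**Conclusion.** The concern holds. Followed as written, 11.7 credits early death in the ICU-days score, and the default Kaplan-Meier display overstates discharge in any arm with deaths before discharge. That Kaplan-Meier overstates discharge does not depend on the assumed figures; how much it does, and both the direction and size of the ICU-days bias, depend on when deaths occur and who enters ICU.

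The usual consequence for ICU days is that the arms look alike. A significant result in favour of the deadlier arm clearly exceeds chance only when deaths are early: 11% at median Day 6 with all survivors in ICU, or about 15% under constant hazards. Reach into 11.9 rests on its lead-in alone, and into 11.5 on a cross-reference that points the wrong way. This should be fixed before unblinding; in an exploratory trial with a separate mortality analysis it does not undermine the trial as a whole.

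**What to change.** 1. In SAP 11.7, for the between-arm comparison, score every death by Day 90, with or without ICU admission, as the worst value (90 days, or 0 days alive and free of ICU), and name a rank-based test.
2. State the same rule explicitly in 11.9 and 11.5, correct the cross-reference in 11.5, and reconcile the highest-or-lowest sentences in 11.7 and 11.9 with it.
3. Keep observed days as a descriptive table, labelled as stay or resource use, and say whether days until death run from ICU admission or from first dose.
4. For time to ICU or hospital discharge, keep deaths as not discharged alive to Day 90 and show cumulative incidence curves in place of Kaplan-Meier with censoring at death. The cause-specific Cox model can stay as supportive.

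The cost is SAP wording and programming, on death, admission and discharge dates already collected. The downside is that death dominates the composite, so it says less about stay among survivors; the descriptive table covers that.
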